1. INTRODUCTION

Background

Medication errors are the leading cause of preventable harm in healthcare settings worldwide (1). An estimated 237 million medication errors occur in England alone every year, with 66 million considered clinically significant (2). There is an estimated cost to the NHS from definitely avoidable adverse drug reactions as a result of these errors of £98.5 million per year, consuming 181,626 bed-days and causing to 712 deaths(2).

Medication related clinical decision support systems, often integrated with electronic prescribing systems, are rapidly increasing in number over the last few decades, ranging from drug-drug interaction alerts to allergy checks and formulary support. A recent systematic review summarised that these systems are still relatively immature, with limited use of patient-specific input or human factors research used to develop them (3). There is an opportunity to improve these systems significantly for the benefit of the user and for patient safety. The World Health Organization propose that interventions to reduce medication error should include the development of technologies that are well understood and designed for the systems and practice they are applied to (1).

Human factors and usability engineering is an integral part of developing medical devices, such as clinical decision support (CDS) systems, to ensure that such devices are easy to use and can be used safely as intended (4). User testing / usability testing, which may incorporate several methods, should be conductive throughout the development process (at formative, summative assessment, and during post-market surveillance) (4). These methods are now becoming more common place in healthcare technology research and should continue to support the development of new technologies (4–7).

RxConnect

RxConnect, a newly registered UKCA marked medical device, is an on-demand clinical decision support tool that receives medication and patient inputs and uses them to filter an underlying formulary, such as the BNF, and perform dosing calculations, as needed, to return patient-specific dosing recommendations. RxConnect does not have a user interface and relies on an integration with third-party systems, such as electronic prescribing systems, to deliver CDS services to clinical end users. For this study a prototype user interface for RxConnect that emulates a typical electronic prescribing system will be used.

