3. STUDY DESIGN

Study Design

A mixed-methods cross-over observational study will be conducted to explore the safety, performance, and user perceptions of utilising RxConnect to support prescribing, in comparison to current practice.

Direct observation of participants will be conducted using multi-angle audio-visual recording, this will be set up behind the computer workstation, to capture the computer display and from above to capture the workstation. The cameras will not be angled to take footage of the participant face. A member of the research team will also be present through the study session.

Prescribing scenarios will be presented on laminated paper along with any relevant patient information, e.g. patient gender, age, weight, diagnosis, relevant medical history, relevant laboratory results.

Intervention arm: Prescribing with RxConnect via a prototype user interface

Participants will be asked to complete a number of practice prescribing tasks whilst *thinking aloud* to describe their thought process and actions. To undertake the prescribing tasks, participants will be asked to use the prototype user interface emulating an electronic prescribing front end, which presents RxConnect medication guidance to the clinical end user (the participant).

Once familiarised with the software workflow, the test prescribing tasks will be given to the participant. For these tasks the participants will be asked to perform the task without the need to think aloud. If the participant wishes to continue to think aloud so long as it doesn't distract

them from completing the task. The medication order the participants have generated using RxConnect support via the user interface will then auto populate a medication order form.

Control arm: Prescribing on Cerner with existing resources

Participants will be asked to perform similarly simple and then complex tasks using their usual practice methods when prescribing. Access will be provided to the prescribers usual electronic prescribing platform, including links to the British National Formulary, Medicines complete, local antimicrobial stewardship application, local intranet, and a generic online search engine. A hard copy of the BNF and BNFc will also be readily available.

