The following outcomes will be measured-

Primary outcome measure-

Number of prescribing errors per scenario

• Subcategorised as - Incorrect drug, dose, route, frequency or patient.

Secondary outcome measures-

- The magnitude of any dose errors (deviation from recommended dosing range)
- Time taken to prescribe each medication
- Prescribers perceived mental load per prescribing scenario
- Hierarchical task analysis
- Qualitative feedback from participants

Number and magnitude of prescribing errors

We define a prescribing error as any of the following errors:

- Incorrect prescribed dose: prescribed doses that deviate from the recommended dose in the BNF/ BNFc or local guideline by more than 10%.
 - If the recommended dose is a range, deviations will be calculated from the max/min
 of the range, whichever is closest to the user calculated dose. If there are multiple
 recommended dose options e.g., from the BNF and from local guidelines, the
 researcher will calculate deviations based on the most appropriate source for the
 indication. When all sources are deemed equally valid, the researcher will record
 the smallest deviation allowed.
 - Magnitude of dosing error will be calculated as a percentage deviation from the recommended dose.
- Incorrect prescribed route: a medication prescribed via a route that deviates from the recommended route for the medication and dose as per the BNF/BNFc or local guidelines.
- Incorrect prescribed frequency: a medication prescribed for a frequency that deviates from the recommended frequency or that accumulated to a total daily dose for the medication and dose as per the BNF/BNFc or local guidelines.
- Incorrect patient: a medication order issued to incorrect patient's electronic medication chart.

Time

The length of time for each prescribing scenario will be calculated from the time the participant begins to read the first scenario, and for subsequent scenarios from the time they complete one scenario and move onto the next.

Task load index

At the end of each scenario the user will be provided with an online NASA TLX (task load index) form to complete (8).

Hierarchical task analysis

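### Where dose sources differ, the researcher picks the reference for scoring errors, and nothing fixes that choice in advance, makes it common to both arms, or hides the arm

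*Combined protocol and SAP*

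**What the plan says.** The primary outcome in section 3 (Study outcome measures) is "Number of prescribing errors per scenario", with dose as one of its subcategories. Under Number and magnitude of prescribing errors, an incorrect dose covers "prescribed doses that deviate from the recommended dose in the BNF/ BNFc or local guideline by more than 10" per cent. If a source gives a range, the deviation is taken from the nearer end.

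The same section expects sources to conflict and gives two rules. First, "the researcher will calculate deviations based on the most appropriate source for the indication". Second, "When all sources are deemed equally valid, the researcher will record the smallest deviation allowed". Both the choice of source and the view that sources are equal are the researcher's to make. The size of a dose error, a secondary outcome, is a percentage deviation from the same recommended dose. Route and frequency are also judged against the BNF/BNFc or local guidelines, with no rule for choosing between them.

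On awareness of arm, section 3 (Study Design) states: "A member of the research team will also be present through the study session". Cameras record the computer display. RxConnect orders fill an order form automatically, while control orders are entered in a Cerner test ward.

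On sources, the Introduction says that RxConnect takes medication and patient inputs and "uses them to filter an underlying formulary, such as the BNF". Control participants have links to the BNF, Medicines Complete, a local antimicrobial application, the intranet and a search engine, with printed BNF and BNFc at hand.

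**The concern.** The reference dose decides whether an order counts as an error. If it is selected once orders are visible, by someone who can tell which system produced them, an unconscious preference can move the primary comparison in either direction. The team's stated hypothesis is that RxConnect is as safe as existing aids, so the scorer is unlikely to be indifferent.

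The choice may also be partly tied to arm. RxConnect rests on a formulary such as the BNF, whereas control participants have the BNF and local guidance. Where the two disagree, choosing one could add errors to one arm more than to the other, even with no bad faith and no inconsistency between orders. The results are meant to inform development before clinical deployment, so a scoring artefact in the error count would matter.

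**Working it through.** **1. What the text fixes.** The plan states no figure to reproduce on this point, so the check begins with the wording. The documents contain no hierarchy of sources, answer key, second rater, adjudication step or masked scorer. The only item described as set in advance is the framework for the hierarchical task analysis. Three ways of applying the rule all fit the text:

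- (a) one source per scenario, chosen before any orders, for both arms: no route to arm-dependent scoring;
- (b) one source per scenario, chosen after orders are seen: scoring is consistent, but the choice can be influenced by which arm it helps;
- (c) a source chosen order by order: the same dose could be scored differently in the two arms.

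The plan does not say which applies.

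**2. When the choice changes a score.** Deviation = |order − reference| / reference, and an error is a deviation above 10%. In abstract units, for an order of 100 that matches one source exactly:

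| Other source | Deviation from it | Scored as |
|---|---|---|
| 125 | 25/125 = 20.0% | error |
| 112 | 12/112 = 10.7% | error |
| 110 | 10/110 = 9.1% | correct |

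An order that follows one source therefore changes status when it lies more than 10% from the other.

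**3. How many orders one decision touches.** Inputs are 30–50 participants (Sample size), equal groups, and Table 1 with three test scenarios per participant in each arm.

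- Orders per arm: 30 × 3 = 90 to 50 × 3 = 150.
- Orders per scenario per arm: 30/2 = 15 to 50/2 = 25.
- Share: 15/90 = 25/150 = 1/6 = 16.7%.

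Step 8 of Appendix 2 gives 4 scenarios, which conflicts with Table 1 and needs reconciling. If it means four per arm, the share is 15/120 = 25/200 = 1/8. If it means four in total, two per arm, the share is 15/60 = 25/100 = 1/4.

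**4. What differential scoring would do if it occurred.** This is an illustration; the documents give none of its rates. Assume no true difference between arms, independent orders, a two-sided 5% test, a true error rate p in both arms, and a share f of RxConnect orders moved from error to correct. With d = f, p̄ = p − f/2 and n orders per arm:

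- se₀ = √(2p̄(1 − p̄)/n)
- se₁ = √([p(1 − p) + (p − f)(1 − p + f)]/n)
- P(significant) = Φ((d − 1.96 se₀)/se₁) + Φ((−d − 1.96 se₀)/se₁)

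For n = 90, p = 0.20 and f = 0.05: se₀ = 0.0566, se₁ = 0.0565, and P = 0.140 + 0.002 = 0.142.

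| f | p assumed | P(significant), n = 90 to 150 |
|---|---|---|
| 0 | 10–30% | 0.05 |
| 2% | 10–30% | 0.06–0.09 |
| 5% | 10–30% | 0.12–0.38 |
| 10% | 20–30% | 0.34–0.68 |

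A share of 5% is 4.5 of 90 or 7.5 of 150 orders, which is 30% of one scenario's orders in one arm (4.5/15 = 7.5/25).

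**The case against.** The strongest reply is that the criterion is the indication. The diagnosis is part of the scenario material and every test scenario is used in both arms, so the natural reading is one source per scenario, the same for everyone. Nothing says that the choice follows the order, that it is made order by order, or that the scorer is the team member in the room. A reader might infer that the protocol has an arm-aware researcher scoring identical orders differently by arm. The documents do not say so; timing and knowledge of arm are inferred from the set-up and from silence.

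Other parts of the reply also stand. Control participants have the BNF as well, and the formulary loaded into RxConnect for this study is not named, so any link between source and arm is partial and its direction unknown. No scenario is shown to have conflicting sources. The 10% tolerance, the nearest-end rule and the smallest-deviation rule already limit the discretion. Recordings and data forms are stored, and data are kept for at least 10 years, so orders could be rescored, although no rescoring is planned. The study calls itself exploratory and says that a sample sufficient for statistical significance is not feasible, which lowers the stakes, although it still plans a chi-square test of error counts by arm.

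What the reply does not supply is any text requiring reading (a). The smallest-deviation rule helps only after the researcher has judged the sources equal, and that judgement is itself open.

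**Conclusion.** The point holds as a gap in what the plan prevents. Where recommended doses differ, the reference for the primary outcome, and for the magnitude of dose error, is a researcher's judgement with no requirement on its timing, its consistency across arms or masking. Arm-dependent scoring is possible but not planned.

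The 1/6 is an upper bound on the share of an arm's orders exposed to one source decision. It assumes Table 1's six scenarios, equal groups, and sources more than 10% apart in one scenario. It is not an estimate of bias. If each arm followed a different source, a key accepting only one of them would still mark the other arm's orders as errors; that effect comes from the sources disagreeing, and the key's contribution is to settle the matter before results are known. The probabilities in the illustration depend wholly on assumed error rates and shares.

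Two further inferences go too far. The number of errors is not the only safety-related outcome, since dose-error magnitude is another, though it shares the weakness. Nor would biased scoring be beyond repair, given the stored recordings. This should be changed before the first session because the remedy is nearly free.

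**What to change.** Before the first session, write and date an answer key for each test scenario, listing every accepted source with its accepted dose or range, route and frequency. The clinical content is for the sponsor to decide.

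In section 3, Number and magnitude of prescribing errors, replace the researcher's choice of source with:

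> Dose, route and frequency are scored against the pre-specified key for the scenario; where the key accepts more than one source, the smallest deviation is used; the same key applies to both arms.

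Apply any later change to a key to all orders for that scenario in both arms, and report it. Reconcile the number of scenarios in Table 1 and Appendix 2 so that the set of keys is complete.

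The cost is a few hours of preparation and the amended wording, with no extra participants or procedures. Once the key is fixed, an unmasked scorer has far less room to influence the result.

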The study team hypothesise that use of RxConnect as a digital prescribing aid is quicker, easier, and as safe to use as currently available prescribing aids. This study aims to utilise user testing to prove or disprove the above hypothesis and to generate quantitative and

qualitative outputs to support the continued development of RxConnect prior to clinical deployment.

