As with the intervention arm, if the participant wishes to continue to think aloud so long as it doesn't distract them from completing the task. Participants will be asked to enter their medication order for the patient within a 'test ward' on the Cerner Millennium Powerchart system.

Order of control vs intervention arm-

Each participant will be randomly assigned to begin with either the control arm or the intervention arm (Group 1 and Group 2, see Table 1). With an equal number of participants being in each group. A random team generator (https://www.randomlists.com/team-generator) will be used for randomisation (see Figure 1) and participants will be assigned their 'participant number' in the order of their participation in the study.

Table 1 - Order of study arms, Group 1 and Group 2

Group 1	Group 2		
Practice 1 (simple) RxConnect	Practice 1 (simple) RxConnect		
Practice 2 (complex) RxConnect	Practice 2 (complex) RxConnect		
Test scenario 1 Control	Test scenario 1 RxConnect		
Test scenario 2 Control	Test scenario 2 RxConnect		
Test scenario 3 Control	Test scenario 3 RxConnect		
Test scenario 4 RxConnect	Test scenario 4 Control		
Test scenario 5 RxConnect	Test scenario 5 Control		
Test scenario 6 RxConnect	Test scenario 6 Control		

Figure 1 Example of participants randomised into two groups

Group 1									
1 Participant 5	2 Participant 43	3 Participant 19	4 Participant 3	5 Participant 34	6 Participant 23				
7 Participant 30	8 Participant 27	9 Participant 21	10 Participant 22	11 Participant 7	12 Participant 1				
13 Participant 10	14 Participant 36	15 Participant 32	16 Participant 26	17 Participant 46	18 Participant 14				
19 Participant 33	20 Participant 31	21 Participant 29	22 Participant 15	23 Participant 47	24 Participant 11				
25 Participant 6									
Group 2									
1 Participant 12	2 Participant 28	- Destisinent OF							
		3 Participant 35	4 Participant 41	5 Participant 44	6 Participant 2				
7 Participant 40			4 Participant 4110 Participant 49						
	8 Participant 38	9 Participant 20		11 Participant 16	12 Participant 37				
13 Participant 39	8 Participant 38 14 Participant 18	9 Participant 2015 Participant 25	10 Participant 49	11 Participant 16 17 Participant 17	12 Participant 37 18 Participant 9				

Sample size

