A target of 30-50 participants is desirable for this descriptive exploratory mixed methods study. This number has been selected pragmatically to account for approximately 5 participants per day over 10 working days.

Sample size sufficient to calculate statistical significance will not be feasible, therefore a power calculation will not be required.

Data collection and management

Data collection

Data will be collected via audio-visual recording which will take place on the SimWard, Paterson Building, St Marys Hospital. A Scotia Medical Observation Training System (smots, Scotia UK, Edinburgh, UK), with two 3- axis, ceiling- mounted video cameras, and three mobile, high-definition cameras equipped with boom microphones, will be used. The cameras will be angles at the computer screen ann onto the workstation and will not take footage of participants faces. Participants will be asked to remove or cover any name badges that may identify them prior to recording commencing.

The researcher will also keep field notes to assist with later analysis of the observations and interviews. The interviews will be transcribed verbatim by the study researcher prior to thematic analysis.

Participant demographic information will be collected via a short 'demographic questionnaire' at the beginning of the user testing session. Nasa Task Load Index questionnaires will be complete by the participant after each of the intervention arms.

Data management

Physical copies of the consent forms and participant list with pseudonymised participant study numbers will be kept within a locked room with swipe card access to the floor of the department.

Audio-visual recordings of the observations and semi-structured interview (See Appendix 1 for a sample interview guide), psuedoanonymised data capture forms and interview transcripts will be stored on an encrypted hard drive and kept in a locked room with swipe card access to the floor of the department. Interview transcripts will use the participant's psuedoanonymous study code in place of their name.

Publication of study findings will not contain identifiable data, participants will be given a study code name and only referred to by their profession and speciality.

Data and all appropriate documentation will be stored for a minimum of 10 years after the completion of the study.

Duration of study

The duration of the study will be six months from the date of the first participant recruited.

Study outcome measures

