Hierarchical task analysis (HTA) will be conducted for each of scenario, a framework will be created apriori based on the anticipated task steps and previous research (9,10), however any additional steps will be added if observed during video analysis. HTA results for participants using RxConnect will be compared to their usual practise.

Qualitative interviews

Following completion of the user testing scenarios, the participant will be invited to take part in a short semi-structured interview regarding their experience of using RxConnect and other more generic questions regarding the use of digital dosing support and indication-based prescribing. (See Appendix 1 for a sample interview guide).

Statistics and data analysis

Sample size

A sample size of 30-50 participants is desirable for this descriptive exploratory mixed methods study. A sample size calculation is therefore not relevant for this study.

Statistical analysis

Categorical data (error counts) from the control arm and intervention arm will be compared using the chi-square test.

Continuous data (magnitude of error, time, task load) will be measured using Mann-Whitney test for non-parametric data.

Sub analysis will explore the effect of possible confounders will be measured using multivariate logistic regression, subject to effect size and sample size limitations.

Variables which may be accounted for include - group number, scenario number, prescribing scenario complexity, prescriber grade, prescriber speciality, control arm or intervention arm.

Hierarchical task analysis

Hierarchical task analysis will be conducted to provide an overview of the prescribing workflow for the control arm and intervention. Vulnerable process steps can be highlighted if they are associated with increased error or time taken when prescribing the scenarios, along with any feedback from participants during practice, observation or in the qualitative interview.

Thematic analysis

Thematic analysis will be conducted using data from throughout the observations and the qualitative interviews (11).

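### Cross-over data are to be compared with independent-sample tests, with no unit of analysis and no participant term, so p-values may be conservative or liberal; the main loss is for time and task load

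*Combined protocol and SAP*

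**What the plan says.** The design is a cross-over with randomised order: "A mixed-methods cross-over observational study will be conducted" and "Each participant will be randomly assigned to begin with either the control arm or the intervention arm" (section 3, Study Design and Order of control vs intervention arm). Table 1 gives every participant six test scenarios, three per arm. Scenarios 1-3 always come first and 4-6 second.

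For the analysis (section 3, Statistical analysis):
- Errors: "Categorical data (error counts) from the control arm and intervention arm will be compared using the chi-square test".
- Other outcomes: "Continuous data (magnitude of error, time, task load) will be measured using Mann-Whitney test for non-parametric data".
- The optional logistic regression may include "group number, scenario number, prescribing scenario complexity, prescriber grade, prescriber speciality, control arm or intervention arm". Participant is not on the list.

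The outcome measures in section 3 record errors and mental load by scenario. They do not say how several orders from one person enter a test, or whether two errors in one order count once or twice.

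Two further places are unsettled. For task load, section 3 (Data collection) says "Nasa Task Load Index questionnaires will be complete by the participant after each of the intervention arms", whereas section 3 (Task load index) and Appendix 2 step 9 have the form completed after every scenario. Appendix 2 step 8 has four scenarios, without saying whether per arm or in total; Table 1 has six.

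**The concern.** Chi-square and Mann-Whitney tests compare two sets of independent observations. Here the same people supply both arms, and several orders each. An analyst following the plan has to choose the unit, and three choices are open:

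- (a) Pool all orders. Independence fails, both within and across arms.
- (b) Take one value per participant per arm and compare unpaired. Both arms hold the same people, and the pairing is ignored.
- (c) Test each scenario separately. This is valid, because within one scenario the arms contain different people, but the samples are small.

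Under (a) or (b) the reported p-values are not at their stated level, and any interval built the same way has the wrong width. The design lets each prescriber act as their own control, and that precision is lost.

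**Working it through.** **Figures in the plan.** There is no alpha, effect size, variance or error rate, so no statistical figure can be reproduced. The only arithmetic is 5 participants a day × 10 days = 50, the top of the 30-50 target.

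**Inputs from the documents.** m = 3 orders per arm per participant (Table 1); 30-50 participants in two equal groups. Pooling therefore gives 6 × 30 = 180 to 6 × 50 = 300 orders, or 90-150 per arm.

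**Assumed inputs.** Two-sided 5%. Errors: control any-error rate 25%, participant SD 0.7-1.2 logits. Task load: residual SD 12, participant SD 8-15, scenario SD 0-8 points. Time: residual log SD 0.3, 10% saving. Participant-by-arm SDs, which describe how much people differ in their response to the tool, are given with each result.

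**Step 1: closed form for pooled orders.** Let rw be the correlation between two orders by one person in the same arm, and rb the correlation across arms. The true variance of the arm difference, relative to what the test assumes, is D = 1 + (m − 1)rw − m·rb. The actual level is 2[1 − Φ(1.96/√D)]. With m = 3:

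| rw | rb | D | Level |
|---|---|---|---|
| 0.2 | 0.2 | 1 + 0.4 − 0.6 = 0.8 | 2.8% |
| 0.5 | 0.5 | 1 + 1.0 − 1.5 = 0.5 | 0.6% |
| 0.3 | 0.2 | 1 + 0.6 − 0.6 = 1.0 | 5.0% |
| 0.3 | 0.1 | 1 + 0.6 − 0.3 = 1.3 | 8.6% |
| 0.3 | 0 | 1 + 0.6 − 0 = 1.6 | 12.1% |

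Break-even is rb = (2/3)rw. Above it the test is conservative, below it liberal. The formula leaves out scenario difficulty. Table 1 balances each scenario across the arms, so difficulty adds to the variance the test assumes but not to the true one. On its own (assumed latent SD 1, error rates 20% and 40%) it takes the chi-square to 1.0-2.1%.

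**Step 2: one value per participant per arm, unpaired.** This is m = 1, so D = 1 − rb. At rb = 0.3, D = 0.7 and the level is 1.9%; at 0.7 it is below 0.1%. This reading is conservative whenever the arms are positively correlated. For task load recorded once per arm, simulated power for a 0.4 SD difference at n = 30 is 21-29%, against 44-77% for an analysis that uses the pairing.

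**Step 3: simulated level of the pooled test, Table 1 layout, n = 30 and 50.**

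| Outcome | Participant effects only | With participant-by-arm variation |
|---|---|---|
| Any error, chi-square | 1.9-4.5% | 3.7-5.5% (SD 0.5 logit); about 5-9% (SD 1.0 in each arm) |
| Time, Mann-Whitney | 0.4-3.4% | 1-8% (log SD 0.1-0.15); 9-14% (0.3) |
| Task load per scenario, Mann-Whitney | about 0-2% | 1-6% (SD 6); about 6-13% (SD 12) |

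If each error counts as a separate unit (1.3-1.7 errors per erroneous order), the chi-square level is 5-13%. A t-test on each participant's difference between scenario sets holds 4.4-5.7% for error counts and 4.0-6.0% for time and task load.

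**Step 4: power, pooled test v set difference.**
- Task load, 5 points, participant effects only: about 30-64% v 76-78% (n = 30); 56-89% v 94-95% (n = 50).
- Time, change from the fix: +7 to +46 points with participant effects only; −6 to +26 at participant-by-arm log SD 0.1-0.15; −9 to −19 at 0.3, where the pooled level is inflated.
- Errors, log OR −0.8, participant effects only, any-error chi-square v count set difference: 35-49% v 35-42% (n = 30); 56-72% v 53-64% (n = 50).

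**Step 5: separate scenario tests.** Each has 30/2 = 15 to 50/2 = 25 orders per arm. For 25% v 14% errors, the variance term is 0.25 × 0.75 + 0.14 × 0.86 = 0.308. At 15 per arm z = 0.11/√(0.308/15) = 0.77 and power is Φ(0.77 − 1.96), about 12%. At 25 per arm z = 0.99 and power is about 17%.

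**Step 6: dose-error magnitude.** At assumed rates of 5-15% there are 0.05 × 180 = 9 to 0.15 × 180 = 27 orders with a dose error at n = 30, and 15 to 45 at n = 50. Few events limit this outcome more than clustering does.

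**The case against.** The strongest reply has four parts.

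First, the study is labelled descriptive and exploratory, states no alpha, plans no interval, and says "Sample size sufficient to calculate statistical significance will not be feasible". That stands as a limit on what is at stake. It does not remove the problem: the plan still names significance tests, and section 1 says "This study aims to utilise user testing to prove or disprove the above hypothesis" while also aiming to inform further development of the tool.

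Second, a reader might infer that the plan intends to pool orders. The documents do not say so. Errors and mental load are measured by scenario, and scenario number is a listed covariate, so separate scenario tests, which are valid, are also open. The finding is that the unit is unstated.

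Third, a reader might infer an inflated false-positive rate. The documents do not support that either. A plain participant effect and differences in scenario difficulty both make the pooled tests conservative. Clear excess for the primary outcome needs strong variation in response. SD 1.0 logit in each arm means an SD of √2 = 1.41 for personal log odds ratios, so 95% of personal odds ratios lie between exp(−1.96 × 1.41), about 0.06, and about 16. The other route is counting several errors in one order as separate units, which the plan neither adopts nor excludes.

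Fourth, the fix does not raise power for the primary outcome. That is correct.

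**Conclusion.** The concern holds in this form: the plan applies independent-sample tests to a cross-over and gives neither a unit of analysis nor a participant term. No other section supplies them. Under pooling the direction of the error cannot be known in advance, and the two forces can cancel. The p-values cannot be read as simply cautious, nor as generally too small.

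For the primary outcome the effect is modest, and what the fix buys is a correct level and a usable interval. The case for change rests mainly on time and task load, where power rises unless participants differ greatly in their response to the tool. All sizes rest on assumed variances and error rates. The consequence is for reported p-values and precision, not for a confirmatory decision. It should be fixed because the change is cheap.

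**What to change.** Replace the two test sentences in section 3 (Statistical analysis):

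- **Main analysis.** For each participant take the difference between scenario set 1-3 and set 4-6 (number of errors, mean log time, mean task load). Compare it between Group 1 and Group 2 by t-test or rank-sum. Half the difference between the group means, with its sign set to RxConnect minus control, is the arm effect; report it with a 95% CI. This removes participant, scenario-set and common period effects. It does not remove differential carry-over: a carry-over of c in one sequence shifts the estimate by c/2, as it does in the pooled analysis.
- **Alternative.** An order-level model with arm and scenario terms and GEE or cluster-robust standard errors by participant.
- **Errors.** Keep the count as primary, with any error yes/no as support. State that several errors in one order are not independent units.
- **Dose-error magnitude.** Report descriptively if events are few, or with the same clustering.
- **Reconcile** when the task-load form is completed (Data collection v Task load index and Appendix 2 step 9), and the number of scenarios (Table 1 v Appendix 2 step 8, saying whether four is per arm or in total).

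Cost: wording and a little analyst time, with no extra participants or data. With participant effects only, the count analysis has about 0-10 points less power than the pooled any-error chi-square.
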